3. STUDY OBJECTIVE AND ENDPOINTS

3.1. Primary Objective

The primary objective of this study is to:

- Evaluate the safety of ataluren as measured by type, frequency, severity, timing, and relationship to study drug of TEAEs, laboratory abnormalities and ECGs

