3.3. Primary Endpoint

The primary endpoints of this study are:

- Overall safety profile in terms of the type, frequency, severity, timing, and relationship to study therapy of any adverse events (AEs) or abnormalities of physical findings, laboratory tests, or ECGs
- Occurrence of any dose-limiting toxicities (DLTs)
- Drug discontinuations due to AEs
- Serious adverse events (SAEs)

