6.3. Safety Monitoring and Study Drug Dose Interruption/Modification

6.3.1. Laboratory Abnormalities and Adverse Events Requiring Evaluation and Potential Drug Interruption/Modification

Patients must be monitored closely for AEs or laboratory abnormalities during the course of the study.

For AEs or laboratory abnormalities, the Investigator will use judgment in determining whether the event or abnormality is clinically significant, whether diagnostic evaluation is warranted, and whether potential interruption of study drug treatment is appropriate. In general, life-threatening (Grade 4) or severe (Grade 3) AEs or laboratory abnormalities should be considered clinically significant, although recurrent or persistent moderate events (Grade 2) may also be considered clinically significant in certain circumstances. Reference should be made to the Common Terminology Criteria for Adverse Events (CTCAE), Version 4.0 (see http://evs.nci.nih.gov/ftp1/CTCAE/CTCAE_4.03_2010-06-14_QuickReference_5x7.pdf) for grading the severity of AEs and laboratory abnormalities.

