9. ADVERSE EVENT ASSESSMENTS

9.1. Adverse Event Definitions

9.1.1. Adverse Events

An AE is any untoward medical occurrence associated with the use of a drug (investigational medicinal product) in humans, whether or not it is considered related to the drug. An AE can therefore be any unfavorable and unintended sign (including an abnormal laboratory finding), symptom, or disease in a study patient who is administered study drug in this study.

For this protocol, untoward medical occurrences that should be reported as AEs include the following:

- All AEs that are suspected or are not suspected to be due to study drug
- Overdose (administration of a study drug dose >4 times the intended total daily dose level for this protocol [>160 mg/kg/day]) of study drug
- All reactions from medication misuse, abuse, withdrawal, sensitivity, or toxicity
- All reactions that result from medication errors or uses of the study drug outside what is described in the protocol
- Apparently unrelated illnesses, including the worsening of a preexisting illness
- Injury or accidents. Note that if a medical condition is known to have caused the injury or accident (a fall secondary to dizziness), the medical condition (dizziness) and the accident (fall) should be reported as 2 separate AEs. The outcome of the accident (hip fracture secondary to the fall) should be recorded in source documents.
- Abnormalities in physiological testing or physical examination findings that require clinical intervention or further investigation (beyond ordering a repeat [confirmatory] test)
- Laboratory abnormalities that require clinical intervention or further investigation (beyond ordering a repeat [confirmatory] test) unless they are associated with an already reported clinical event. Laboratory abnormalities associated with a clinical event (eg, elevated liver enzymes in a patient with jaundice) should be captured in the source documents. Laboratory abnormalities not requiring clinical intervention or further investigation will be captured as part of overall laboratory monitoring, and should not be reported as AEs.

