11.7.2. Laboratory Parameters

Hematological and biochemistry data will be summarized by visit and will be graded according to CTCAE severity grade, when applicable. The frequencies of the worst severity grade observed will be displayed. For variables graded according to CTCAE severity grade, the frequencies of

the worst severity grade observed will be displayed. For parameters for which a CTCAE scale does not exist, the frequency of patients with values below, within, and above the normal ranges will be summarized. In the by-subject analysis, a patient having the same abnormality more than once will be counted only once based on the worst severity grade observed.

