12.2. Clinical Laboratory Assessments

Laboratory assessments performed during each study visit and will include hematology, biochemistry and urinalysis. The presentation of laboratory results focuses on the descriptive summaries at Baseline, each scheduled follow-up evaluation, and the change from baseline. All subjects in the Safety Population who have a baseline and at least one follow-up laboratory assessment will be included in the presentation of the laboratory data. In order for a subject to be included in the analysis for a particular laboratory test, the subject must have a baseline value and a follow-up laboratory assessment for the laboratory test. Unscheduled laboratory evaluations will be presented in the listings. The summarized results will be presented for the 4 week primary PK period of the study and for the extension study data.

For each quantitative laboratory parameter, the baseline results will be summarized using descriptive statistics: n, mean, SD, median, and range. Only paired quantitative data will be summarized in the tables; all data will be presented in the listings. Results will be summarized and presented in Tables 14.3.6.1 entitled *Summary of Hematology Results by Visit* (Safety Population), 14.3.6.2 entitled *Summary of Biochemistry Results by Visit* (Safety Population), and 14.3.6.3 entitled *Summary of Urinalysis Results by Visit* (Safety Population).

Laboratory shift tables will be prepared and presented based on the normal reference ranges and presented by parameter and the scheduled observation time. Shift tables will be prepared and presented for each quantitative hematology parameter in Table 14.3.6.4 entitled *Hematology Shift Table Results by Visit* (Safety Population). Shift tables will be prepared and presented for each quantitative biochemistry parameter in Table 14.3.6.5 entitled *Biochemistry Shift Table Results by Visit* (Safety Population). Shift tables will be prepared and presented for each

quantitative urinalysis parameter in Table 14.3.6.6 entitled *Urinalysis Shift Table Results by Visit* (Safety Population).

The supportive data for Tables 14.3.6.1 through 14.3.6.6 are presented in Listing 16.2.8.4 entitled *Hematology Results*, Listing 16.2.8.5 entitled *Biochemistry Results*, and Listing 16.2.8.6 entitled *Urinalysis Results*. These listings will be sorted by subject number, parameter, and relative day.

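### The SAP drops, without giving a reason, the per-patient worst-CTCAE-grade laboratory summary that the protocol specifies for part of the primary safety endpoint

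*SAP*

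**What the plan says.** Protocol 11.7.2 sets the laboratory analysis: "Hematological and biochemistry data will be summarized by visit and will be graded according to CTCAE severity grade, when applicable". It requires worst-grade frequencies to be displayed and gives the counting rule: "a patient having the same abnormality more than once will be counted only once based on the worst severity grade observed". The normal-range summary is the fallback: "For parameters for which a CTCAE scale does not exist, the frequency of patients with values below, within, and above the normal ranges" is what it asks to have summarized there.

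SAP 12.2 plans by-visit descriptive statistics (Tables 14.3.6.1 to 14.3.6.3), shift tables (14.3.6.4 to 14.3.6.6) and a by-visit summary of abnormal results (14.3.6.7). On the shift tables it says: "Laboratory shift tables will be prepared and presented based on the normal reference ranges and presented by parameter and the scheduled observation time". It sends unscheduled laboratory evaluations to the listings. The output list in SAP Section 14 contains no laboratory table by CTCAE grade.

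The primary objective in protocol 3.1 reads "Evaluate the safety of ataluren as measured by type, frequency, severity, timing, and relationship to study drug of TEAEs, laboratory abnormalities and ECGs", and the first primary endpoint in protocol 3.3 covers the type, frequency and severity of adverse events or "abnormalities of physical findings, laboratory tests, or ECGs".

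**The concern.** A by-visit table cannot apply a rule that counts each child once across visits. A shift against the normal range shows direction but not severity: a child who starts above the range stays in the same cell however far the value rises. CK illustrates this, because inclusion criterion 6 already requires it to be elevated.

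The omission also does not read as a considered decision. Where SAP 11.2 drops the terminal rate constant and half-life, it cites the protocol and gives a reason. For adverse events, SAP 12.1.3.3 keeps the maximum grade per subject. For laboratory data the grade disappears without comment.

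At stake is a table showing how many children ever reached each grade of each laboratory abnormality. The protocol promised that summary for part of its primary safety endpoint.

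**Working it through.** The plan states no figure for this point, so the check compares the texts and then bounds what by-visit counts can say.

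**1. Protocol 11.7.2 against SAP 12.2 and Section 14**

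| Protocol element | In the SAP? |
|---|---|
| Summary by visit | Yes |
| Below/within/above normal where no CTCAE scale exists | Yes, but applied to all quantitative parameters |
| CTCAE grading of hematology | No |
| CTCAE grading of biochemistry | No, except as action thresholds for some analytes in SAP Table 3 |
| Worst-grade frequencies | No |
| Each patient counted once at worst grade | No (kept for adverse events only) |
| Reason for the change | None found |

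Laboratory tables giving a worst CTCAE grade per child: 0 of 7.

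**2. Does Table 14.3.6.7 fill the gap?** It is by visit, which is enough to rule it out as a once-per-child count. The SAP does not say outright that the Table 3 cut-offs following it define its content. If they do:

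- No hematology parameter appears.
- Of the biochemistry panel in protocol 8.2.7.2, 12 analytes appear: total bilirubin, GGT, ALT, cystatin C, creatinine, BUN, sodium, potassium, magnesium, calcium, phosphorus and bicarbonate.
- Nine carry a grade label; ALT, cystatin C and BUN do not.
- One of the nine, creatinine, has a Grade 1 cut-off. The Grade 1 column is blank in all 10 electrolyte rows.
- None of the nine separates Grade 3 from Grade 4: bilirubin and GGT pool from Grade 3 upward, creatinine pools from Grade 2 upward, and the six electrolytes pool Grades 3 and 4.

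The documents do not say how many of the remaining analytes have a CTCAE scale, so I give no number.

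**3. Do the adverse event tables fill the gap?** SAP 3.4.1 says abnormal laboratory tests are reported as adverse events. Protocol 9.1.1 is narrower: "Laboratory abnormalities not requiring clinical intervention or further investigation will be captured as part of overall laboratory monitoring, and should not be reported as AEs". Abnormalities that need action therefore reach the graded adverse event tables; the others can appear only in laboratory outputs. Protocol 6.3.1 says that, in general, "life-threatening (Grade 4) or severe (Grade 3) AEs or laboratory abnormalities should be considered clinically significant", so the group left out is mainly Grade 1 and isolated Grade 2.

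**4. What by-visit counts can tell the reader**

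Scheduled post-baseline visits: one in the 4-week period (Day 28), then five (Days 112, 196, 280, 364 and 392). If each of V visits shows k of n children at a grade, the number ever at that grade lies between k (the same children each time) and min(n, V × k) (different children each time).

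- 4-week period, V = 1: the bounds coincide, so repeat counting is not a problem. Only the grade and any unscheduled values are missing.
- After Day 28, V = 5, n = 12, k = 1 (assumed): 1 to 5 children; 1/12 = 8%, 5/12 = 42%.
- After Day 28, V = 5, n = 12, k = 2 (assumed): 2 to 10 children; 2/12 = 17%, 10/12 = 83%.

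These are arithmetic limits for assumed counts, not forecasts.

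**The case against.** The strongest reply is that little of importance is hidden. The primary analysis is the 4-week period, where a single post-baseline visit already counts each child once. Abnormalities needing action enter the adverse event tables at maximum grade, and hepatic and renal events also have their own once-per-subject table (14.3.1.7). The laboratory signal the protocol names, Grade 1 hypercreatinemia (about 15% of patients in Study 009, protocol 6.3.2), is the one for which Table 3 has a Grade 1 band. A confirmatory repeat of an abnormal scheduled value adds something only if it is worse. With about 12 children in a descriptive single-arm study, a reader can count from listings sorted by subject, parameter and day. Protocol 11.7.2 asks only for worst-grade frequencies, not for a shift from baseline grade or for two time windows.

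Most of this stands as a limit on size. It does not remove the mismatch. The creatinine band still gives by-visit counts, and transient events may fall at different visits in different children. The SAP does not say the listings carry a grade, so a reader might have to grade each value before counting. The baseline-grade layout and the two windows do go beyond the protocol's minimum. They are recommended because they separate new from pre-existing abnormalities and match the split that SAP 12.2 already uses.

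**Conclusion.** The concern holds. The SAP departs from protocol 11.7.2 on part of the primary safety endpoint, and no planned output restores the missing summary. The effect is moderate: abnormalities needing action are not lost, and repeat counting arises only after Day 28. What is missing is the number of children ever at each grade, chiefly for low-grade abnormalities needing no action, and any tabulation of values obtained between scheduled visits. This should be corrected, but it does not threaten the study's main safety conclusions.

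The conclusion rests on the SAP text available: its front pages were not, but Section 12.2 and the full output list were, and neither gives a reason. The percentage ranges rest on assumed per-visit counts and a sample of 12.

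**What to change.** Add one table to SAP 12.2 and Section 14: baseline grade by worst post-baseline CTCAE v4.0 grade, Safety Population, for every hematology and biochemistry parameter with a CTCAE scale. Count each subject once, use scheduled values plus any unscheduled values in the study database, and show the 4-week period and the whole study. List the parameters without a scale; the planned normal-range shifts serve those. Keep all seven by-visit tables. If the omission was deliberate, the SAP should instead state why.

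As a minor alignment, reword SAP 3.4.1 so that only laboratory abnormalities meeting the protocol 9.1.1 rule are reported as adverse events.

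The cost is one table shell and two wording edits. Hematology and biochemistry are already collected at every scheduled visit, so no new data are needed.

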12.3. Vital Signs

All vital signs will be taken each visit and include the following parameters:

- Pulse Rate (beats per minute)
- Temperature (°C)
- Respiratory Rate (breaths/min)
- Systolic Blood Pressure (mmHg)
- Diastolic Blood Pressure (mmHg)

Vital signs will be summarized for each clinical assessment using the summary statistics of n, mean, SD, median, and range. These summaries will be presented for the subjects who have data at baseline and the specific follow-up visit. The summarized results will be presented for the 4 week primary PK period of the study and for the extension study data. The organization of the

results is commensurate with the organization of the laboratory data. All subjects in the Safety Population who have a baseline and at least one follow-up vital sign assessment will be included in the presentation of the data. In order for a subject to be included in the analysis for a particular evaluation, the subject must have a baseline value and a follow-up assessment. Unscheduled laboratory evaluations will be presented in the listings. The summarized results will be presented for the 4 week primary PK period of the study and for the extension study data. The results will be presented in Table 14.3.3 entitled *Summary of Vital Sign Results by Visit* (Safety Population). The supportive data listing is Listing 16.2.8.1 entitled *Vital Signs*. This listing will be sorted by subject number, parameter, and relative day.

12.4. Electrocardiogram Results

ECGs will be taken at Screening, Day 28, Day 364, and at the 4 week follow-up visit (Visit 7 - Study Day 392) and include the classification of the findings *Normal*, *Abnormal*, *Clinically Significant*, and *Abnormal, Not Clinically Significant*. The results at each time point will be summarized using counts and percentages.

Shift tables for each digital ECG parameter will be prepared and presented by time point using the matched pairs for the qualitative interpretation of the ECG measurements. Results will be presented in Table 14.3.4 entitled *Electrocardiogram Shift Table Results by Visit* (Safety Population). The number and percentage of subjects will be presented.

The supportive data for the ECG tables are presented in Listing 16.2.8.2 entitled *Electrocardiogram Results*. This listing will be sorted by subject.

12.5. Physical Examination Results

A physical examination will be performed for all subjects at Screening, at the 4 week follow-up visit (Visit 7 / Study Day 365), and whenever it is clinically indicated. Any findings or absence of findings relative to each subject's physical examination will be documented in the subject's eCRF. All subjects in the Safety population will be included in Table 14.3.5 entitled *Summary of Physical Examination Results* (Safety Population). This table will summarize the subject population with respect to 12 specific physical characteristics:

- Cardiovascular system
- Chest and lungs
- Thyroid
- Abdomen
- Nervous System
- Skin and mucosae
- Musculoskeletal
- Eyes, Ears, Nose, Mouth, Throat
- Spine
- Lymph Nodes
- Extremities
- Genitourinary

For each characteristic, the number and percentage of subjects found to be abnormal will be presented. The supportive data for Table 14.3.5 will be presented in Listing 16.2.8.3 entitled *Physical Examination Results*. This listing will be sorted by subject number and relative day; unscheduled physical examinations will be presented in the listings.

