In patients with DMD, the age at which the earliest sign or symptom of the disease is noted ranges from infancy to approximately 6 years old [Ciafaloni 2009]. Initial signs and symptoms of DMD include lordosis, a waddling gait, and the Gowers' sign (a characteristically abnormal method of rising from a supine to a standing position) [Brooke 1989, McDonald 1995, Boland 1996, Worton 2001]. Inexorable progressive weakness is seen, particularly in the proximal musculature. Ambulation becomes increasingly abnormal. By the age of 8 years, most boys have difficulty rising from the floor and ascending stairs and they often fall while walking. Boys with the disease spend less time walking and walk more slowly than healthy boys [McDonald 2005a], and are significantly less active than normal boys of similar age [McDonald 2002, McDonald 2005b]. By 10 to 14 years of age, most are wheelchair-bound. In ambulatory boys with DMD, the most frequent cardiac abnormality is sinus tachycardia and heart rate variability, occurring from childhood and persisting throughout life [Finsterer 2003, Gulati 2005]. Pulmonary function is usually normal before 10 years of age and is well maintained into adolescence in boys receiving corticosteroids [Mendell 1989, Griggs 1991, Phillips 2001, Tangsrud 2001, Biggar 2001, Biggar 2006]. Later in adolescence, cardiac and diaphragmatic muscles become progressively weaker and patients require treatment for cardiac insufficiency and ventilatory support. Patients usually die of cardiac or pulmonary failure by 15 to 22 years of age [Brooke 1989, McDonald 1995, Simonds 1998, Worton 2001, Eagle 2002].

Presently, ataluren is the only therapy available to restore dystrophin protein production and preserve muscle function. The current standard of care is corticosteroids, which do not address the underlying cause of the disease and are not typically initiated prior to the age of 5 years old.

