8.2.5. Height, Weight and Physical Examination

Height (in cm) and weight (in kg) will be measured at all study visits. A full physical

examination (including evaluation of the cardiovascular system, chest and lungs, thyroid, abdomen, nervous system, skin and mucosae, musculoskeletal system, eyes, ears, nose, mouth, throat, spine, lymph nodes, and extremities) will be conducted at Screening (Visit 1) and 4-week Follow-up (Visit 8), 4 weeks after discontinuation of study drug.

Physical examinations may also be performed at any time during the study as clinically indicated.

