11.7.4. Other Safety Parameters

Physical examination data will be described. Where appropriate, changes from baseline will be presented by visit.

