- Table 14.3.1.2.2 Summary of Adverse Events that Occurred in the 4-Week Follow-up Phase by System Organ Class and Preferred Term (Safety Population)
- Table 14.3.1.3 Summary of Treatment-Emergent Adverse Events by System Organ Class, Preferred Term, and Severity (Safety Population)
- Table 14.3.1.4 Summary of Treatment-Emergent Adverse Events by Descending Incidence of Preferred Term (Safety Population)
- Table 14.3.1.5 Summary of Treatment-Emergent Adverse Events by System Organ Class, Preferred Term, and Relationship to the Study Medication (Safety Population)
- Table 14.3.1.6 Summary of Treatment-Emergent Adverse Events Leading to Discontinuation of the Study Drug by System Organ Class and Preferred Term (Safety Population)
- Table 14.3.1.7 Summary of Treatment-Emergent Adverse Events Associated with Specific Toxicities by System Organ Class and Preferred Term (Safety Population)
- Table 14.3.1.8 Summary of Serious Treatment-Emergent Adverse Events by System Organ Class and Preferred Term (Safety Population)
- Listing 14.3.2.1 Serious Treatment-Emergent Adverse Events
- Listing 14.3.2.2 Treatment-Emergent Adverse Events Leading to Discontinuation of Study Drug
- Listing 14.3.2.3 Treatment-Emergent Adverse Events Associated with Specific Toxicities

- Table 14.3.3 Summary of Vital Sign Results by Visit (Safety Population)
- Table 14.3.4 Electrocardiogram Shift Table Results by Visit (Safety Population)
- Table 14.3.5 Summary of Physical Examination Results by Visit (Safety Population)
- Table 14.3.6.1 Summary of Hematology Results by Visit (Safety Population)
- Table 14.3.6.2 Summary of Biochemistry Results by Visit (Safety Population)
- Table 14.3.6.3 Summary of Urinalysis Results by Visit (Safety Population)
- Table 14.3.6.4 Hematology Shift Table Results by Visit (Safety Population)
- Table 14.3.6.5 Biochemistry Shift Table Results by Visit (Safety Population)
- Table 14.3.6.6 Urinalysis Shift Table Results by Visit (Safety Population)
- Table 14.3.6.7 Summary of Abnormal Laboratory Results by Visit (Safety Population)
- Listing 14.3.7.1 Abnormal Hematology Values
- Listing 14.3.7.2 Abnormal Biochemistry Values
- Listing 14.3.7.3 Abnormal Urinalysis Values

4. Patient Data Listings

- Listing 16.2.1 Subject Disposition
- Listing 16.2.2 Protocol Deviations
- Listing 16.2.3.1 Inclusion and Exclusion Criteria
- Listing 16.2.3.2 Eligibility Criteria
- Listing 16.2.4.1 Demographics and Subject Characteristics

-
- Listing 16.2.4.2 Medical History

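### Table 14.3.5 counts abnormal boys per body system with no within-boy comparison to screening, so the table does not identify newly abnormal boys

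*SAP*

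**What the plan says.** SAP section 12.5 plans one statistic for the physical examination: "For each characteristic, the number and percentage of subjects found to be abnormal will be presented". In that section Table 14.3.5 is "entitled *Summary of Physical Examination Results* (Safety Population"), with no mention of visit. The output list in SAP section 14 has it as "Table 14.3.5 Summary of Physical Examination Results by Visit (Safety Population"). Listing 16.2.8.3 supports the table, is ordered by subject and relative day, and includes unscheduled examinations.

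Protocol section 11.7.4 reads: "Physical examination data will be described. Where appropriate, changes from baseline will be presented by visit".

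Protocol section 3.3 and SAP section 3.4.1 both put abnormal physical findings in the first primary endpoint, beside adverse events, laboratory tests and ECGs. SAP section 3.4.1 says each body system is rated normal or abnormal.

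On timing, Protocol section 8.2.5 says the full examination "will be conducted at Screening (Visit 1) and 4-week Follow-up (Visit 8"), and otherwise examinations are done as clinically indicated. SAP section 12.5 places the second scheduled examination "at the 4 week follow-up visit (Visit 7 / Study Day 365").

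**The concern.** A boy whose system was already abnormal at screening counts in Table 14.3.5 exactly as a boy whose system became abnormal on treatment. In this disease that matters. Protocol section 2.1 says "Initial signs and symptoms of DMD include lordosis, a waddling gait", and adds Gowers' sign. Rows such as musculoskeletal and spine may therefore largely describe the disease before dosing. For a safety endpoint, the number of interest is how many boys were normal at screening and abnormal later, and the planned statistic does not give it.

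Two smaller faults sit in the same section. The visit and day attached to the follow-up examination do not match the schedule, and the list of body systems differs from the one in SAP section 3.4.1.

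**Working it through.** The plan states no figure to reproduce. The check compares the texts and then asks what the planned counts can and cannot tell the reader.

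**1. Is a comparison with screening specified elsewhere in the SAP?**

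| Data | Section | Comparison with baseline |
|---|---|---|
| Laboratory | SAP 12.2 | Paired summaries, change from baseline, shift tables |
| Vital signs | SAP 12.3 | Limited to boys with baseline and follow-up values |
| ECG | SAP 12.4 | Matched-pair shift table |
| Physical examination | SAP 12.5 | None stated |

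The general convention in SAP section 5 does not fill the gap. It defines change as the post-baseline value minus the baseline value, which does not apply to a normal/abnormal rating.

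**2. What would by-visit counts show?** Let n boys be examined at both visits, with *a* abnormal at screening and *b* abnormal at follow-up. Let *S* be the number abnormal at both. *S* lies between max(0, a + b − n) and min(a, b). The newly abnormal number is b − S, so it lies between max(0, b − a) and min(b, n − a).

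If visits are pooled into one ever-abnormal count, that count is a plus the newly abnormal number, so it lies between max(a, b) and min(n, a + b).

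Take n = 12 from the planned sample size (Protocol section 11.1, SAP section 3.5). The values of *a* and *b* are assumed for illustration:

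| a | b | Newly abnormal | Pooled count |
|---|---|---|---|
| 0 | 1 | 1 | 1 |
| 2 | 2 | 0 to 2 | 2 to 4 |
| 6 | 6 | 0 to 6 | 6 to 12 |
| 8 | 8 | 0 to 4 | 8 to 12 |
| 9 | 10 | 1 to 3 | 10 to 12 |
| 10 | 10 | 0 to 2 | 10 to 12 |
| 12 | 12 | 0 | 12 |

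For 8 and 8: max(0, 8 − 8) = 0 and min(8, 12 − 8) = 4. By-visit counts fix the newly abnormal number only at extremes, such as no boy abnormal at screening. A pooled count merges pre-existing and new findings.

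**3. Visit label.** The schedules in Protocol section 8.1 and SAP section 16 put the follow-up examination at Visit 8, Day 392, and schedule none at Visit 7. The visit and day in SAP section 12.5 are therefore wrong. SAP section 12.4 has a similar slip: it gives the follow-up ECG the right day, 392, but calls it Visit 7.

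**4. Body systems.** SAP sections 3.4.1 and 12.5 each list 12 entries and share 11. The twelfth is Other in section 3.4.1 and Genitourinary in section 12.5. Protocol section 8.2.5 names neither.

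**The case against.** The strongest reply is that little is hidden. In a study of about 12 boys, Listing 16.2.8.3 lets a reader follow each boy's results. Protocol section 9.1.1 makes an examination finding an adverse event if it needs intervention or investigation beyond a repeat test. SAP section 12.1.1 counts worsening of a pre-existing condition as an adverse event. Such findings reach the treatment-emergent tables, which separate new or worsened events from old ones. The study is single-arm and descriptive, and no decision rule uses Table 14.3.5.

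That stands, and it rules out several stronger readings that a reader might infer:

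- *The table takes no account of screening.* The section 14 title says by visit. The documents show conflicting titles and no shift.
- *New abnormalities cannot be seen at all.* They can, in the listing and often in the adverse event tables. They cannot be identified from Table 14.3.5.
- *The SAP breaches Protocol section 11.7.4.* That provision is conditional, so it is better described as not implemented.
- *A musculoskeletal row would read 12/12 whatever happened.* This assumes every boy is abnormal at screening and that visits are pooled. By visit, a resolution would lower the follow-up count.
- *The wrong visit label loses every scheduled post-baseline examination.* The sentence itself says 4-week follow-up; only the parenthesis is wrong.
- *Findings recorded under Other are lost.* The documents do not show whether the eCRF collects that category, and any entries would fall under the listing.

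The reply does not cover a new finding that falls below the adverse event threshold. That finding may appear only in a listing, although the endpoint names physical findings in addition to adverse events.

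**Conclusion.** The concern holds as a gap in one summary table for part of a primary endpoint. SAP section 12.5 specifies no within-boy comparison with screening, and the by-visit layout in section 14 would not supply one. With 12 boys and 8 abnormal at each visit, the table would be compatible with 0 to 4 newly abnormal boys. That range assumes the counts shown and complete examinations at both visits; other counts give wider or narrower ranges.

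No data are lost and no inference is biased. The consequence is that the safety summary does not state a number the endpoint calls for, leaving the reader to build it from the listing. Because the ratings already exist, the change is worth making.

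A shift has its own limit. A binary rating cannot show worsening in a system already abnormal at screening. If all 12 boys were abnormal in a row at screening, the newly abnormal count would be 0 by construction.

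**What to change.** In SAP section 12.5:

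1. Title Table 14.3.5 by visit, matching section 14.
2. Add a screening-to-post-baseline shift for each body system (normal to abnormal, abnormal to abnormal, abnormal to normal). Report the newly abnormal count, with boys normal at screening and examined later also shown as a denominator.
3. Add a note that boys already abnormal in a system at screening are to be read with Listing 16.2.8.3 and the adverse event data.
4. Correct the follow-up label to Visit 8 / Day 392.
5. Reconcile the body-system list with SAP section 3.4.1, Protocol section 8.2.5 and the eCRF, settling Genitourinary against Other.

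The cost is SAP wording and one revised table shell. No new data are needed.
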